# 9.1. Sample Size Calculation

This study will randomize a total of 450 subjects in the Phase 2 and Phase 3 portions of the study. Subjects who have provided written informed consent at the time the enrollment goal in either phase is reached may complete Screening and be randomized if they meet all eligibility criteria, at the discretion of the Sponsor or its representatives.

# Phase 2 Sample Size

A total of 140 subjects will be randomized in a 1:1 ratio to receive either CMP-001 in combination with nivolumab (Arm A) or nivolumab monotherapy (Arm B). A sample size of 140 subjects provides 80% power to detect an absolute treatment difference of 25% with a 2-sided alpha level of 0.05, assuming that the ORR in Arm A is 65% and the ORR in Arm B is 40%. The sample size calculation is performed in PASS-2020 for testing 2 independent proportions using the continuity corrected Z-test with pooled variance.

# Phase 2/3 Sample Size

If there is a statistically significant treatment difference at a 2-sided alpha level of 0.05 for the ORR at the end of Phase 2, an additional 310 subjects will be randomized in a 1:1 ratio to receive either CMP-001 in combination with nivolumab (Arm A) or nivolumab monotherapy (Arm B). Combined with the 140 subjects enrolled in Phase 2, this will make up the overall Phase 3 study population sample size of 450 subjects.

The Phase 3 sample size of 450 subjects is calculated to compare the PFS by BICR between the 2 treatment arms at an alpha level of 0.05 (2-sided). The final PFS analysis will be performed when at least 331 PFS events have been observed across the 2 treatment arms (PD by BICR review or death from any cause). With 331 PFS events, the study has 90% power to demonstrate a treatment effect in PFS at a 0.05 alpha level (2-sided) when the true HR is 0.70. The smallest treatment effect that can be detected statistically significant in this study is HR 0.805. The sample size calculation is performed in PASS-2020.

# 9.2. Multiplicity

In order to preserve the family-wise type I error rate of 5% (2-sided), the gatekeeping strategy will be applied.

The 5% (2-sided) alpha is allocated to ORR primary analysis at end of Phase 2. If the treatment effect on ORR at end of Phase 2 is statistically significant at a 2-sided alpha level of 0.05, then enrollment in Phase 3 may be triggered. The 5% (2-sided) alpha will be recycled to the Phase 3 primary analysis of PFS. The detailed testing hierarchy including the secondary endpoints will be pre-specified in the SAP. The overall type I error rate for this study will be strictly controlled at 5% (2-sided).

# 9.3. Analysis Sets

The main analysis sets are defined in this section. The Phase 2 analysis sets apply to subjects who are randomized or treated in the Phase 2 portion of the study. The Phase 3 analysis sets apply to all subjects who are randomized or treated in both the Phase 2 portion and Phase 3 portion of the study. Additional analysis sets may be defined in the SAP.

# 9.3.1. Intent-to-Treat Analysis Set

The Intent-to-Treat (ITT) Analysis Set is defined as all subjects who are randomized.

# 9.3.2. Safety Analysis Set

The Safety Analysis Set is defined as all subjects who receive at least 1 dose of study treatment.

# 9.3.3. Per Protocol Analysis Set

The Per Protocol Analysis Set is defined as all subjects who are randomized and are without major protocol deviations.

# 9.3.4. Pharmacodynamic Analysis Set

The Pharmacodynamic Analysis Set is defined as all subjects who receive at least 1 dose of CMP-001 and have at least 1 measurable sample at Baseline and at least 1 evaluable biomarker sample after CMP-001 administration.

# 9.4. Background Characteristics

# 9.4.1. Disposition

The number and percentage of subjects who screen fail, are randomized in the study, are treated in the study, discontinue study treatment, and who discontinue the study will be summarized by treatment arm. The primary reason for treatment and study discontinuation will also be summarized.

Subject disposition will be presented in a by-subject data listing.

# 9.4.2. Demographics and Other Baseline Characteristics

Demographics and other Baseline characteristics (age, sex, race, ethnicity, body weight, height, and body mass index) will be summarized by treatment arm using descriptive statistics for the ITT Analysis Set and listed by subject.

# 9.4.3. ECOG Performance Status

ECOG data will be presented in a by-subject data listing. Change from Baseline in ECOG Performance Status will be summarized by treatment arm for the ITT Analysis Set.

# 9.4.4. Melanoma History

Melanoma history (time since initial diagnosis, tumor stage, nodal status, and metastatic disease status at time of initial diagnosis), and PD-L1 status will be summarized by treatment arm using descriptive statistics for the ITT Analysis Set and listed by subject.

#### 9.4.5. Prior Cancer Treatments

All prior melanoma treatments will be captured in the EDC separately from other prior medications. A summary of the number of prior lines of cancer therapy will be generated for the ITT Analysis Set by treatment arm.

# 9.4.6. Medical and Surgical History

Medical and surgical history will be listed by subject. Medical history will be coded using MedDRA.

#### 9.4.7. Protocol Deviations

All protocol deviations will be captured electronically and presented in a by-subject data listing. All deviations will be reviewed on an ongoing basis and classified as major or minor.

#### 9.4.8. Prior and Concomitant Medications

Prior medications are those taken within 30 days of the first dose of study treatment and discontinued before the first dose of study treatment.

Concomitant medications will be assessed continually from 30 days before the first dose of study treatment (W1D1) through 100 days after the last dose of study treatment (both CMP-001 and nivolumab) or until an alternative cancer treatment is initiated, whichever occurs first. Treatment medications for AEs related to study treatment that occur more than 100 days after the last dose of study treatment will be collected.

Medications will be coded using the World Health Organization drug dictionary and summarized by treatment arm according to the Anatomical Therapeutic Chemical (ATC) class and preferred term for each dose group for the Safety Analysis Set. Subjects will be counted only once for a given concomitant medication for each ATC class and preferred term in the summary tables.

Concomitant medications will be presented in a by-subject data listing.

# 9.5. Study Treatment Exposure and Compliance

The number of CMP-001 and nivolumab doses received by each subject will be summarized descriptively by treatment arm for the Safety Analysis Set. The duration of each treatment, dose intensity, and relative dose intensity will also be summarized.

CMP-001 dosing, including date and time of each dose, route of administration, dose administered, location of each injection, and the volume injected into each tumor at each dosing visit will be presented in a by-subject data listing.

Nivolumab dosing, including date, time, and dose administered, will be presented in a by-subject data listing.

# 9.6. Efficacy Analyses

The efficacy analyses will be based on the ITT Analysis Set and may also be performed for the Per-Protocol Analysis Set if deemed appropriate. Phase 3 efficacy analyses will be performed based on the results of the end of Phase 2 primary endpoint results, as described in Figure 3.

End of Phase 3 analyses performed, including Phase 3 Phase 3 primary endpoint Yes enrollment (PFS) and secondary is triggered. and exploratory endpoint analyses. End of Phase 2 IDMC review ORR and safety data. Phase 3 go/no-go criterion (Phase 2 ORR p<0.05) is met. No Phase 3 enrollment occurs. Additional exploratory safety No and efficacy analyses may be performed for Phase 2.

Figure 3: Go/No-Go Decision Tree Based on End of Phase 2 Efficacy

Abbreviations: IDMC = Independent Data Monitoring Committee; ORR = objective response rate; PFS = progression-free survival.

# 9.6.1. Confirmed Objective Response Rate

The primary efficacy endpoint for the Phase 2 portion of the study is the confirmed ORR based on RECIST v1.1 as determined by BICR.

The confirmed ORR is defined as the proportion of subjects in the analysis set who have confirmed best overall response (BOR) as CR or PR. The confirmed ORR will be calculated as the number of subjects with a confirmed CR or PR divided by the number of subjects in the analysis population [ORR = (confirmed CR + confirmed PR)/# subjects] in each treatment group for the ITT Analysis Set.

ORR will be analyzed using a 2-sided Cochran-Mantel-Haenszel test stratified by stage and PD-L1 expression to compare the 2 treatment arms. Associated odds ratio and 95% CI will also be calculated. Additionally, ORR and the 95% exact CIs will be calculated using the Clopper-Pearson method for each of the 2 treatment arms. The secondary endpoint DCR and the 95% Clopper-Pearson CIs will be summarized as well.

The BOR is defined as the best response designation based on RECIST v1.1 as determined by BICR. Subjects who discontinue due to death due to disease progression, or disease progression, prior to having a post-Baseline tumor assessment will be classified as having a best response of PD. Subjects who discontinue prior to having a post-Baseline scan for other reasons will be counted as non-responders in the ITT analyses.

Objective response rate based on RECIST v1.1 as determined by BICR will be evaluated as a secondary endpoint in the Phase 3 portion of the study. Objective response rate per RECIST v1.1 and iORR per iRECIST by Investigator assessment will also be summarized.

#### 9.6.2. Progression-Free Survival

The primary endpoint in the Phase 3 portion of the study, PFS, will be analyzed using a 2-sided log-rank test stratified by stage and PD-L1 expression to compare the 2 treatment arms. All subjects enrolled in the Phase 3 portion of the study (including subjects also treated in Phase 2) will be included in this analysis. HRs and corresponding 2-sided 95% CIs will be estimated using a Cox proportional hazards model, with treatment arm as a single covariate, stratified by the above factors. PFS curves, PFS medians with 95% CIs, and PFS rates at 6 and 12 months with 95% CIs will be estimated using Kaplan-Meier methodology.

PFS is defined as the time from date of randomization to the date of documented progressive disease based on RECIST v1.1 by BICR or death from any cause, whichever occurs first (FDA-2018). Subjects who are alive and progression-free at the time of analyses will be censored in the analyses. Additional censoring rules may be defined in the SAP.

Analysis of PFS and iPFS based on RECIST v1.1 and iRECIST determined by Investigator assessment will also be performed.

#### 9.6.3. Overall Survival

Overall survival will be calculated from the date of randomization to death from any cause (FDA-2018). Subjects who are alive at the time of analyses will be censored at the time of last study contact. Median OS will be calculated using the Kaplan-Meier method for each treatment arm OS will be analyzed using the same approach as PFS.

#### 9.6.4. Disease Control Rate

The confirmed disease control rate is defined as the proportion of subjects in each treatment arm in the analysis set who have a confirmed best response of CR or PR, or SD lasting at least 4 months. Per RECIST v1.1, CR or PR must be confirmed by a confirmatory assessment performed at least 4 weeks after the initial response. In the case of stable disease, measurements must have met the SD criteria at least once after study entry at a minimum interval of 6 weeks. Disease control rate (DCR) will be analyzed in a similar manner as ORR.

# 9.6.5. **Duration of Response**

Duration of response (DOR) will be based on RECIST v1.1 as determined by BICR and calculated for responders.

The DOR will be measured from the time at which criteria are first met for CR or PR (whichever is first recorded) until the first date that recurrence or PD is objectively documented (taking as reference for PD the smallest measurements recorded on study). The duration of overall CR is measured from the time measurement criteria are first met for CR until the first date that recurrent disease is objectively documented. Censoring details will be described in the SAP, including handling of subjects who continue to be followed for PTFU disease assessments.

Duration of response (DOR) and iDOR will also be determined by Investigator assessment per RECIST and iRECIST.

Duration of response (DOR) will be analyzed using the same approach as PFS.

# 9.6.7. Post-Progression Disease Response

Post-progression disease assessments of tumor response based on iRECIST by Investigator assessment will be summarized for each treatment arm.

# 9.7. Safety Analyses

The assessment of safety will be based on the following assessments: AEs, clinical laboratory tests, vital sign measurements, ECGs, and physical examinations.

# 9.7.1. Adverse Events

Treatment-emergent AEs (TEAEs) will be coded using MedDRA and data will be summarized by treatment arm for the Safety Analysis Set. The number and percent of subjects reporting each TEAE will be summarized, as well as the number of TEAEs. A subject with 2 or more TEAEs within the same level of summarization (ie, system organ class [SOC] or preferred term) will be counted only once in that level using the most severe event or most related (for the relationship to study treatment tables).

Additional summary tables will be generated for Grade 3 or higher TEAEs, TEAEs considered related to treatment (possibly, probably, or definitely), TEAEs by maximum grade and relationship, TEAEs resulting in death, SAEs, related SAEs, and TEAEs leading to treatment discontinuation.

A by-subject AE data listing, including verbatim term, SOC, preferred term, treatment, grade, outcome, and relationship to treatment for CMP-001 and nivolumab, will be generated.

Separate listings will also be generated for Grade ≥3TEAEs, TEAEs considered related to study treatment (possibly, probably, or definitely), TEAEs resulting in death, SAEs, and TEAEs leading to treatment discontinuation.

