- e. CMP-001 dosing will begin on W1D1. Weekly dosing: A window of ±2 days is permitted for CMP-001 dosing from W2D1 to W7D1. The first dose of CMP-001 may be administered SC or IT, at the discretion of the Investigator; all subsequent doses are planned to be administered IT until no injectable lesions remain. Subjects must complete all 7 weekly CMP-001 doses before moving to the Q3W dosing schedule. Q3W dosing (W10D1+): A window of ±3 days is permitted for CMP-001 dosing from W10D1 throughout the trial. When nivolumab is permanently discontinued due to an immune related AE, CMP-001 must also be permanently discontinued. Refer to Section 5.3 for Treatment Compliance.
- f. Nivolumab dosing will begin on W1D1 and continue Q3W throughout the study for a maximum of 2 years. For subjects in Arm A, when CMP-001 injection and nivolumab dosing fall on the same day, CMP-001 injection will be given before nivolumab dosing. Refer to Section 5.1.1 for Nivolumab Dosing.
- g. A full physical examination (PE) will be conducted at Screening and EOT. If the Screening full PE is performed >72 hours before the W1D1 visit, then a brief (symptom directed) PE must be performed within 72 hours before the first injection of CMP-001. Brief PEs focused on areas of disease or AEs must be performed at the W1D1, W3D1, W7D1 CMP-001 injection visits, at every CMP-001 injection visit thereafter, and at any other time as clinically indicated. Height will be obtained at Screening only and weight will be obtained at all PE assessments.
- h. Vital signs include measurement of blood pressure (systolic and diastolic blood pressure), respiratory rate, heart rate, and body temperature. Blood pressure and heart rate should be taken in the seated position following ≥3 minutes of rest. For subjects in Arm A, for the first 6 CMP-001 dosing visits (W1D1 to W6D1), vital signs must be collected prior to the CMP-001 injection and at 30-minute (±15 minutes) intervals for 4 hours after CMP-001 injection. Starting at W7D1, observation periods may be reduced to a minimum of 1 hour following CMP-001 injection at the Investigator's discretion based on the AE profile of the individual subject. When vital signs are scheduled at the same time as collection of a blood sample, the vital sign measurements should be obtained before the scheduled phlebotomy. If a study visit occurs where only nivolumab is administered, vital signs must be collected before the start of the nivolumab infusion.

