## 7.4. Safety Assessments

Safety will be assessed on an ongoing basis throughout this study. All safety assessments and AEs will be recorded on the appropriate eCRF and reported to the Sponsor or its representatives (as applicable). All AEs/SAEs will be assessed continually from the time of informed consent through 100 days after the last dose of study treatment (both CMP-001 and nivolumab) or until an alternative cancer treatment is initiated, whichever occurs first, for all subjects. All other medical occurrences (non-adverse events) that begin before the start of study treatment should be recorded on the Medical History/Current Medical Conditions section of the eCRF, not the AE section. All AEs reported on or after the date that study treatment was first administered (W1D1), will be recorded on the eCRF and will be considered treatment-emergent adverse events (TEAEs). All TEAEs, defined as an AE that started or worsened in severity on or after the date that study treatment was first administered (W1D1), will be graded according to CTCAE v5.0 (Appendix C) and coded using Medical Dictionary for Regulatory Activities (MedDRA). Worsening TEAEs (ie, increase to higher severity/grade) should be recorded as new AEs. Ongoing AEs with a decrease in severity/grade do not need to be captured as new AEs. Subjects who discontinue CMP-001 but remain on treatment with nivolumab will continue to have AEs collected according to this schedule until 100 days after the last dose of nivolumab or until an alternative cancer treatment is initiated, whichever occurs first.

Abnormal vital sign measurements, clinical laboratory test results, and/or physical examination findings deemed clinically significant by the Investigator may be repeated, until the value returns to Baseline, within normal limits (WNL), or reaches a clinically stable endpoint, as determined by the Investigator. Any post-Baseline abnormal findings that are considered clinically significant by the Investigator will be recorded on the AE page of the eCRF. The Investigator is responsible for reviewing all clinical laboratory results.

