# 8. SAFETY DATA COLLECTION, RECORDING, AND REPORTING

#### 8.1. Adverse Events

### **8.1.1.** Definition of an Adverse Event

An AE is an untoward or medical occurrence associated with the use of study treatment (active or placebo drug, biologic, or device) in clinical investigation subjects, which does not necessarily have a causal relationship with the study treatment. An AE can therefore be any unfavorable and unintended symptom, sign, disease, condition, or test abnormality whether or not considered related to study treatment (Appendix C). Adverse events that do not meet the definition for an SAE are considered non-SAEs.

Adverse events should be recorded upon first occurrence and followed until resolution. A persistent AE is continuous and does not resolve between Q3W dosing visits. The AE is documented only once unless the grade becomes more severe. If the grade becomes more severe, the AE must be reported again with the new grade. Any recurrent AE should be reported as new AE.

Adverse events include:

- Changes in health status described by the subject or signs observed by the Investigator or medical staff.
- Test abnormalities (eg, laboratory tests) that result in an alteration in medical care (diagnostic or therapeutic) and/or are considered clinically significant by the Investigator.

Immune-mediated adverse events are AEs consistent with an immune-mediated mechanism or immune-mediated component for which non-inflammatory etiologies (eg, infection or tumor progression) have been ruled out. IMAEs can include events with an alternate etiology, which were exacerbated by the induction of autoimmunity. Information supporting the assessment will be collected on the subject's eCRF.

Every AE must be assessed by the Investigator with regard to whether it is considered immune-mediated. For events that are potentially immune-mediated, additional information will be collected on the subject's eCRF.

Disease progression and associated hospitalization, are not considered AEs or SAEs in this study.

Abnormalities present at Baseline will be recorded as medical history and will only be considered AEs if they reoccur after resolution or worsen during the study.

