## 8.2.1. Adverse Event Severity/Grade

For each recorded AE or SAE, the Investigator or designee must provide an assessment of severity/grade using the CTCAE v5.0 (Appendix C).

Note that severity is not the same as "seriousness" (defined in Table 4). Seriousness (not severity) serves as a guide for defining regulatory reporting obligations.

Worsening of an ongoing TEAE (ie, an increase to higher grade) should be recorded as a new AE. Ongoing AEs that decrease in severity/grade should not be captured as new AEs.

**Table 5:** CTCAE Adverse Event Grades

Classification	Definition
Grade 1	Mild; asymptomatic or mild symptoms; clinical or diagnostic observations only; intervention not indicated
Grade 2	Moderate; minimal, local, or non-invasive intervention indicated; limiting age-appropriate instrumental activities of daily living
Grade 3	Severe or medically significant but not immediately life-threatening; hospitalization or prolongation of hospitalization indicated; disabling; limited self-care activities of daily living
Grade 4	Life-threatening consequences: urgent intervention indicated
Grade 5	Death related to adverse event

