- (2) Planned dose intensity (mg/week) will be calculated as the total planned cumulative dose to be received divided by the planned duration of treatment (weeks) based on the protocol schedule.

Planned Duration of Treatment (weeks) = number of planned treatments * 3 (weeks)

(3) Relative dose intensity (%) will be calculated based on the actual cumulative dose received relative to the planned cumulative dose throughout the duration of treatment as follows:

Relative dose intensity (%) = (actual dose intensity / planned dose intensity) * 100%

3. Dosage Modifications

The number and percentage of subjects with dose delayed, withheld, interrupted, reduced, permanently withdrawn will be tabulated with the reasons for each treatment arm, respectively.

Dosing of CMP-001 and nivolumab, including date and time of each dose, route of administration, dose administered, location of each injection, and the volume injected into each tumor at each dosing visit will be presented in a by-subject data listing per the information from the study drug administration eCRFs.

B. Adverse Events

An AE is an untoward or medical occurrence associated with the use of study drug (active or placebo drug, biologic, or device) in subjects of clinical investigation, which does not necessarily have a causal relationship with the study drug. An AE can therefore be any unfavorable and unintended symptom, sign, disease condition, or test abnormality whether or not considered related to study drug. AEs that do not meet the definition for a Serious Adverse Event (SAE) are considered non-SAEs.

AEs should be recorded upon the first occurrence and followed until resolution. A persistent AE is continuous and does not resolve between Q3W dosing visits. The AE is documented only once unless the grade becomes more severe. If the grade becomes more severe, the AE must be reported again with the new grade.

Regeneron Pharmaceuticals Inc. / Protocol: CMP-001-011 IQVIA Biotech (Confidential) Project # SZA58924

Specifically, worsening of an ongoing TEAE (i.e., an increase to higher grade) should be recorded as a new AE. Ongoing AEs with a decrease in severity/grade do not need to be captured as new AEs. Any recurrent AE should be reported as new AE each time the AE occurs.

According to Protocol section 8.1.1, disease progression, and associated hospitalizations and deaths, are not considered an AE or SAE in this study.

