All other medical occurrences (non-adverse events) that begin before the start of study treatment administration should be recorded on the Medical History/Current Medical Conditions section of the eCRF, not the AE section.

Adverse events starting beyond 100 days after the last dose of the study treatment should not be recorded on the AE eCRF unless they are considered treatment-related SAEs.

Serious adverse events and AEs resulting in discontinuation will be followed until one of the following occurs:

- The event resolves
- The event stabilizes
- The event returns to a baseline value if a baseline value is available
- The event can be attributed to agents other than the study drug or to factors unrelated to study conduct
- The Investigator and Medical Monitor agree that follow-up is no longer necessary

Adverse event (AE) data are available to the Sponsor from two sources, i.e., the eCRFs and the SAE paper forms and corresponding SAE narratives. While reconciliation will be performed to ensure consistency between the two types of data, the production of data summaries and listings will be based on the data collected on the eCRF.

1. Treatment-emergent adverse event (TEAE)

A TEAE is defined as an AE that started or worsened in severity on or after the date and time (if date is the same) when the study treatment was first administered (W1D1) until 100 days after the last dose of the study treatment or until the initiation of an alternative new anti-cancer treatment, whichever occurs first. For cases in which treatment-emergence could not be ascertained, the event will be classified as treatment-emergent. Pre-treatment AEs are AEs that occur from the time of the informed consent prior to the first dose of study treatment (W1D1).

Regeneron Pharmaceuticals Inc. / Protocol: CMP-001-011 IQVIA Biotech (Confidential) Project # SZA58924

TEAEs will be coded using MedDRA (version 23.1 or later) and data will be summarized by treatment arm for the Safety Analysis Set. The number and percentage of subjects reporting any TEAEs will be summarized, as well as the number of TEAEs. A subject with more than one TEAEs within the same level of summarization (i.e., system organ class [SOC] or preferred term [PT]) will be counted only once in that level using the highest severity grade and the strongest causal relationship to study drug for the purposes of the incidence tabulations.

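### The planned number of TEAEs counts records rather than events, because an episode that worsens is counted again at each rise in grade

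*Protocol*

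**What the plan says.** **Recording.** Protocol 8.1.1 treats a persistent AE as one continuous event, documented once unless its grade rises. In that case: "If the grade becomes more severe, the AE must be reported again with the new grade". Protocol 8.2.1 repeats the rule: "Worsening of an ongoing TEAE (ie, an increase to higher grade) should be recorded as a new AE". So does Protocol 7.4: "Worsening TEAEs (ie, increase to higher severity/grade) should be recorded as new AEs". SAP IX.B carries it over: "worsening of an ongoing TEAE (i.e., an increase to higher grade) should be recorded as a new AE". Falls in grade are handled differently: "Ongoing AEs with a decrease in severity/grade do not need to be captured as new AEs". Only upward steps therefore create extra records.

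**Counting.** Protocol 9.7.1 plans, by treatment arm: "The number and percent of subjects reporting each TEAE will be summarized, as well as the number of TEAEs". SAP IX.B.1 plans the same: "The number and percentage of subjects reporting any TEAEs will be summarized, as well as the number of TEAEs". Both sections add that a subject with several TEAEs in the same system organ class or preferred term is counted once at that level, at the highest grade. The SAP ties this rule to the incidence tabulations. Neither document gives a corresponding rule for the number of events.

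**Observation.** In Arm A, Protocol Table 1 note h requires vital signs before each of the first 6 CMP-001 injections and then "at 30-minute (±15 minutes) intervals for 4 hours after CMP-001 injection". Protocol 5.1.2.2 requires at least 4 hours of observation after each of those injections.

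**The concern.** The recording rule splits one continuous episode into several AE records, and the counting rule adds up the records. The result will be read as a number of adverse events, but it also reflects how many upward grade steps each event took and how many of those steps were noticed and written down. Two subjects with the same worst grade of the same event can contribute different counts.

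Safety is the first-listed secondary endpoint in SAP IV.B, and the arms hold 9 and 11 subjects (SAP II.C). In arms that small, a handful of split records can move a raw total visibly, and a reader has no means of telling split records from distinct events.

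**Working it through.** The documents state no TEAE count, no records-per-episode figure and no worsening rate, so there is no planned figure to reproduce. The check applies the recording and counting rules together and then asks what follows for the comparison of arms.

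**Step 1: records per episode.** Records = 1 + number of recorded upward grade steps.

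| Course of one continuous episode | Records counted as TEAEs | Subjects counted | Maximum grade |
|---|---|---|---|
| Starts and stays at Grade 3 | 1 | 1 | 3 |
| Grade 2, then 3 | 2 | 1 | 3 |
| Grade 1, then 2, then 3 | 3 | 1 | 3 |

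The last two columns do not change, so the subject-incidence and maximum-grade tables are sound. Only the event count moves.

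**Step 2: inflation within one arm.** If m is the mean number of worsening records per episode, the reported count is (1 + m) times the number of episodes. The documents do not give m. Assumed values of 0.1, 0.3 and 0.5 give counts 10%, 30% and 50% above the number of episodes.

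**Step 3: distortion of the Arm A to Arm B ratio.** With equal numbers of true episodes, distortion = (1 + mA)/(1 + mB). All values of m are assumptions.

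| mA | mB | Distortion |
|---|---|---|
| 0.10 | 0.30 | 1.10/1.30 = 0.85 |
| 0.10 | 0.10 | 1.10/1.10 = 1.00 |
| 0.25 | 0.10 | 1.25/1.10 = 1.14 |
| 0.40 | 0.10 | 1.40/1.10 = 1.27 |
| 0.50 | 0.10 | 1.50/1.10 = 1.36 |

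Equal rates leave the ratio undistorted whatever their size, and reversed rates push it below 1.

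**Step 4: is there a documented reason for mA to exceed mB?** Readings every 30 minutes for 4 hours make 8 after each injection. With the pre-dose set, Arm A has 6 × (1 + 8) = 54 scheduled sets of vital signs from W1D1 to W6D1. Assuming that Arm B attends the same six visits with one set at each, it has 6. Denser observation in Arm A is therefore documented. A higher rate of recorded worsening per episode is not.

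**The case against.** Four points can be made against the concern.

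1. **The count follows the plan's own definitions.** Both documents define a TEAE as an AE that starts or worsens after first dose, and both say that each worsening is a new AE. This stands as far as it goes: the number would be reproducible. It would still not be a number of distinct events, and Protocol 8.1.1 itself describes a persistent AE as continuous.

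2. **Little depends on the figure.** The overview lines listed in SAP IX.B.1 are all numbers of subjects. No event rate and no test of event counts is planned, and SAP VI describes the analyses as primarily descriptive and exploratory. This stands and limits the weight of the point.

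3. **Bias against Arm A is not shown.** A reader might infer from the 4-hour observation periods that double counting is more frequent in Arm A and that the comparison is tilted against CMP-001. The inference is plausible, since Protocol 5.1.3.2 expects fever and hypotension within 1 to 4 hours of injection, which is the window being watched. The documents do not support it as a conclusion. They give no escalation rates. AE monitoring in Table 1 is not split by arm, and note i sets one collection rule for all subjects. A vital-sign finding becomes an AE only if the Investigator judges it clinically significant (Protocol 8.3). Arm B cannot be described as having readings at nivolumab visits only, because Table 1 marks vital signs at every visit from W1D1 to W7D1 without an arm split.

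4. **Careless linkage could create its own error.** Up to 3 tumors may be injected at one visit (Protocol 5.1.2.3.1), so joining on preferred term alone could merge separate injection-site events, which can arise only in Arm A. SAP VI.C imputes partial dates to the limits of the month or year or to the first dose date, which can create false overlaps. The outcome categories in Protocol Table 7 include no closure for worsening. These points stand and shape the fix.

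**Conclusion.** The point holds as a defect in how one safety figure is defined. Under the rules as written, an episode that worsens once or twice adds 2 or 3 to the number of TEAEs, and one that never worsens adds 1. This follows from the text and needs no assumption. It applies only to episodes that worsen and only to the event count.

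The overall size is unknown because no worsening rate is given. For assumed means of 0.1 to 0.5 worsening records per episode, the count exceeds the number of episodes by 10% to 50%. The effect on the comparison of arms cannot be derived in either direction: the assumed range runs from 0.85 through 1.00 to 1.36. No conclusion that the plan disadvantages CMP-001 should be drawn from it.

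The change is worth making because the label misdescribes the number and the correction is cheap. The analysis concerned is an ancillary, descriptive one in 20 subjects.

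**What to change.** In SAP IX.B.1, derive the number of TEAEs on linked episodes:

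- Decide treatment emergence record by record first, so that a pre-treatment condition that worsens on treatment still counts as a TEAE.
- Within a subject, join TEAE records that share the preferred term and also the verbatim term or site, when the higher-grade record starts while the earlier one is ongoing or on the day it ends.
- Use recorded dates, not imputed ones, to decide on a join. Leave a pair unjoined if its recorded dates do not settle the matter.
- Count each joined episode once, at its maximum grade. Count a recurrence after resolution as a further TEAE.
- Keep the record-level listing unchanged.

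Where linkage is not possible, label the figure as the number of AE records. No protocol amendment is needed for the analysis, since SAP I.B says that the SAP governs where the two differ.

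The cost is one derivation rule and a small amount of programming. Protocol 8.3 already has onset, resolution and severity recorded for every AE, although the eCRF should be checked for how a worsened record is closed and whether site is captured. The downside is that ambiguous links stay unjoined, so some overcounting may remain; a footnote should say so. The rule does not change how often recurrent events are counted.
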